7 JUNE 2019

CLINICAL STUDY PROTOCOL

A RANDOMIZED, CONTROLLED, DOUBLE-BLIND STUDY TO EVALUATE THE EFFICACY AND SAFETY OF AN INTRA- ARTICULAR INJECTION OF AMPION™ IN ADULTS WITH PAIN DUE TO SEVERE OSTEOARTHRITIS OF THE KNEE

STUDY NUMBER: AP-013

Drug Development Phase:	Phase 3
Investigational Product:	Ampion™
Indication:	Osteoarthritis of the knee
Sponsor:	Ampio Pharmaceuticals, Inc. [name]
Lead Investigators:	[name]
Date:	Version 1.0 7 June 2019

Conduct: In accordance with the ethical principles that originate from the Declaration of Helsinki and that are consistent with International Conference on Harmonisation (ICH) guidelines on Good Clinical Practice (GCP) and regulatory requirements as applicable.

Confidential Information

This document is the sole property of Ampio Pharmaceuticals, Inc. This document and any and all information contained herein has to be considered and treated as strictly confidential.

This document shall be used only for the purpose of the disclosure herein provided. No disclosure or publication shall be made without the prior written consent of Ampio Pharmaceuticals, Inc.

PROTOCOL SIGNATURE PAGE

I have read and understand the contents of this clinical protocol for Study AP-013 dated 7 June 2019 and agree to meet all obligations of Ampio Pharmaceuticals, Inc. as detailed in all applicable regulations and guidelines.

Signed By:

<Study personnel signature>

<Enter date>

PROTOCOL SYNOPSIS

Sponsor: Ampio Pharmaceuticals, Inc.	Investigational Product: Ampion™	Developmental Phase: Phase 3
Title of Study: A Randomized, Controlled, Double-Blind Study to Evaluate the Efficacy and Safety of an Intra-Articular Injection of Ampion in Adults with Pain Due to Severe Osteoarthritis of the Knee		
Protocol Number: AP-013		
Study Center(s): Approximately 20 sites		
Lead Investigators: [name]		
Indication: Pain of severe osteoarthritis of the knee (OAK)		
Number of patients: This trial is designed for 1,034 patients, 517 per study arm, randomized 1:1 for Ampion and saline intra-articular (IA) injection. There will be an interim analysis at 724 patients, 362 per study arm, randomized 1:1, Ampion and saline. A promising zone design is used with the possibility to increase the sample size by 1.5 times the original sample size up to 1,552 patients at the interim analysis.		
Objectives: The co-primary trial objectives are to evaluate the greater efficacy for pain improvement and function improvement of 4 mL Ampion versus saline intra-articular (IA) injection, when applied to patients suffering from severe osteoarthritis of the knee (OAK). Efficacy will primarily be assessed with WOMAC A pain and WOMAC C function scores. The secondary trial objectives include the following evaluations of an intra-articular injection of Ampion, as compared to saline, when administered to patients suffering from severe OAK: assessment of safety; improvement in the Patient Global Assessment; and the amount of rescue analgesia.		

Sponsor: Ampio Pharmaceuticals, Inc.	Investigational Product: Ampion™	Developmental Phase: Phase 3
Exploratory objectives are to analyze the effect, if any, of the efficacy of Ampion, as compared to saline, on stiffness; Outcome Measures in Rheumatology Clinical Trials and Osteoarthritis Research Society International (OMERACT-OARSI) responder status; proportion of treatment failures; change in pain and function as a cumulative distribution function (CDF) plot; and a Bayesian meta-analysis for WOMAC A pain sub score including KL 4 patients from studies AP-003-A, AP-003-B, AP-003-C, AP-004, and AP-013.		
Methods: Study AP-013 is a randomized, controlled, double-blind study with a 28-day screening period for each patient followed by a 24-week participation period. This trial will use an adaptive design with promising zone method for sample size re-estimation. This trial is designed for 1,034 patients, 517 per study arm, randomized 1:1 for Ampion and saline IA injection. There will be an interim analysis to allow for sample size re-estimation up to 1.5 times the original trial size for a maximum of 1,552 patients, 776 per study arm, randomized 1:1 for Ampion and saline IA injection. The clinical effects of treatment on severe OAK will be evaluated at 2, 4, 6, 8, 10, 12, and 24 weeks, using the Western Ontario and McMaster Universities Arthritis Index (WOMAC®) osteoarthritis Index 3.1, and the Patient's Global Assessment of disease severity (PGA). Average daily WOMAC A pain scoring will be collected for seven days using a daily diary beginning one week prior to clinic visits at Week 0 (baseline) and Week 12, in order to determine a WOMAC A weekly pain score for Baseline and Week 12. Safety will be assessed by recording adverse events (through 24 hours post-dose and at all follow up contacts) and physical examination and vitals (Baseline, Weeks 6, 12, and 24).		
Diagnosis and Main Criteria for Inclusion: 
1. Able to provide written informed consent to participate in the study2. Willing and able to comply with all study requirements and instructions of the site study staff3. Male or female, 40 years to 85 years old (inclusive)4. Must be ambulatory5. Index knee must be symptomatic for greater than 6 months with a clinical diagnosis of OAK and supported by radiological evidence (Kellgren-Lawrence Grade 4) that is not older than 6 months prior to the date of screening6. Moderate to moderately-severe OA pain in the index knee (rating of at least 1.5 on the WOMAC Index 3.1 as measured by 5-point Likert Pain Subscale) assessed at screening7. Ability to temporarily discontinue nonsteroidal anti-inflammatory drug (NSAID) for 48 hours prior to scheduled clinical efficacy evaluations8. No analgesia (including acetaminophen [paracetamol]) taken 12 hours prior to an efficacy measure		

Sponsor: Ampio Pharmaceuticals, Inc.	Investigational Product: Ampion™	Developmental Phase: Phase 3
9. No known clinically significant liver abnormality (e.g. cirrhosis, transplant, etc.).		
Main Criteria for Exclusion: 
1. As a result of medical review and screening investigation, the Principal Investigator considers the patient unfit for the study2. A history of allergic reactions to human albumin (reaction to non-human albumin such as egg albumin is not an exclusion criterion)3. A history of allergic reactions to excipients in 5% human albumin (N-acetyltryptophan, sodium caprylate)4. Presence of tense effusions5. Inflammatory or crystal arthropathies, acute fractures, history of aseptic necrosis or joint replacement in the affected knee, as assessed locally by the Principal Investigator6. Isolated patella femoral syndrome, also known as chondromalacia7. Any other disease or condition interfering with the free use and evaluation of the index knee for the duration of the trial (e.g. cancer, congenital defects, spine osteoarthritis)8. Major injury to the index knee within the 12 months prior to screening9. Severe hip osteoarthritis ipsilateral to the index knee10. Any pain that could interfere with the assessment of index knee pain (e.g. pain in any other part of the lower extremities, pain radiating to the knee)11. Any pharmacological or non-pharmacological treatment targeting OA started or changed during the 4 weeks prior to randomization or likely to be changed during the duration of the study12. Use of the following medications:
a. No IA injected pain medications in the study knee during the studyb. No analgesics containing opioids. NSAIDs may be continued at levels preceding the study, however may not be used 48 hours prior to efficacy evaluations, and acetaminophen is available as a rescue medication during the study from the provided supplyc. No topical treatment on osteoarthritis index knee during the studyd. No significant anticoagulant therapy (e.g. Heparin or Lovenox) during the study (treatment such as Aspirin and Plavix are allowed)e. No systemic treatments that may interfere with safety or efficacy assessments during the studyf. No immunosuppressantsg. No use of corticosteroids > 10 mg prednisolone equivalent per dayh. If corticosteroid use is ≤ 10 mg prednisolone equivalent per day, and if clinically indicated, subjects should be allowed to decrease their corticosteroid use. Additionally, some subjects may need to increase their steroid dose to treat worsened symptoms in the treated knee, and subjects who increase their corticosteroid dose above their starting dose of corticosteroid during the study will be treated as “treatment failures” for efficacy analysis13. No human albumin treatment in the 3 months before randomization or throughout the duration of the study		

Sponsor: Ampio Pharmaceuticals, Inc.	Investigational Product: Ampion™	Developmental Phase: Phase 3
Test Product, Dose and Mode of Administration: Ampion, 4 mL, single intra-articular injection in the knee		
Reference Therapy, Dose and Mode of Administration: Saline, 4 mL, single intra-articular injection in the knee		
Study Duration: 24 weeks		
Criteria for Evaluation: Safety: Adverse events, physical examination, and vitals Efficacy: WOMAC osteoarthritis Index 3.1 and PGA		
Statistical Methods: The co-primary efficacy endpoints are the change from Baseline to Week 12 in the WOMAC A pain score and the WOMAC C function score. The primary efficacy analysis will use the intent-to-treat (ITT) analysis population with the per-protocol (PP) analysis population as supportive. WOMAC A pain and WOMAC C function scores will be analyzed using mixed-effects models with repeated measures (MMRM) with treatment assignment, week, and baseline WOMAC A pain scores and WOMAC C function scores, respectively, as covariates, with comparisons between Ampion and saline. All treatment emergent adverse events (TEAEs) will be reported by randomization assignment. There will be no statistical tests for incidence and severity of TEAEs.		

TABLE OF CONTENTS

PROTOCOL SYNOPSIS	3
LIST OF ABBREVIATIONS AND DEFINITION OF TERMS.....	11
1 INTRODUCTION.....	13
1.1 Study Drug.....	14
1.2 Background to the Disease	14
1.3 Previous Human Experience	15
1.4 Preclinical Data	15
1.4.1 Pharmacology Studies	15
1.4.2 Toxicity and Safety Studies.....	16
1.5 Clinical Experience	16
2 RATIONALE FOR THE STUDY	19
2.1 Rationale for the Doses and the Dosing Regimen.....	19
3 STUDY DESIGN	20
3.1 Study Design Overview.....	20
3.2 Study Objectives.....	21
3.2.1 Primary Objective.....	21
3.2.2 Secondary Objectives	21
3.2.3 Exploratory Objectives	21
3.3 Safety Monitoring Committee.....	21
3.4 Stopping Rules.....	22
3.5 Study Endpoints.....	22
3.5.1 Co-Primary Endpoint.....	22
3.5.2 Secondary Endpoints	22
3.5.3 Exploratory Endpoints.....	22
3.6 Blinding and Randomization.....	23
3.7 Code-breaking	23
4 SELECTION OF PATIENTS	24
4.1 Number of Patients	24
4.2 Recruitment Methods	24
4.3 Inclusion Criteria	25
4.4 Exclusion Criteria	25
4.5 Inclusion of Patients Incapable of Giving Informed Consent	26
5 STUDY PLAN AND PROCEDURES	27
5.1 Description of Study Visits	27
5.1.1 Visit -1 (Day -28 through Day 0, in-clinic): Screening.....	27

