3.3 Safety Monitoring Committee

A Safety Monitoring Committee (SMC) will be established to review the safety of Ampion as the study progresses. The SMC will consist of independent clinicians and statisticians not involved in the conduct of the clinical trial. The Medical Monitor will attend open sessions of the SMC meetings. The SMC will be primarily responsible for reviewing any serious Adverse Event (SAE) and other clinically important safety findings (e.g., discontinuations due to AEs) that may occur during the study. Prior to unblinding any treatment assignments, a charter will be developed to detail the SMC review responsibilities, the frequency of meetings, and data evaluation plans.

A promising zone analysis will be run after outcomes are available for 724 patients (70% of final sample size). The promising zone analysis will be run for WOMAC C since function will be the predominant determinant of sample size.

The SMC, with the exclusion of the Medical Monitor, will also be tasked with evaluating whether sample size increase criteria has been met for the interim efficacy analysis. The SMC committee will review the interim analyses and report the next steps to the Sponsor, which will include one of the following prespecified actions: (1) continue to a total of 1,034 patients, 517 patients per study arm, randomized 1:1 for Ampion and saline IA injection; (2) sample size re-estimation up to 1.5 times the original trial size for a total of 1,552 patients, 776 per study arm, randomized 1:1 for Ampion and saline IA injection, has occurred using the promising zone and the new sample size will be reported.

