10.3.4 Statistical Analysis of Co-Primary Effectiveness Endpoints

A mixed-effects model with repeated measures (MMRM) will be used to test the main effect of change in WOMAC A weekly pain score (determined as the average of Daily Pain measurements taken at Baseline and Week 12) from Baseline of Ampion vs. saline at 12 weeks. The model will include change from Baseline measures at 2, 4, 6, 8, 10, and 12 weeks. Treatment assignment, week, and Baseline WOMAC A measure will be included as fixed effects. Patient ID will be included to capture repeated measures using a compound symmetric covariance matrix for residuals. The primary hypothesis test for pain is the change in pain at 12-weeks at the one-sided $\alpha = 0.025$ level.

The same model will be used to test the effect of WOMAC C function change from Baseline of Ampion vs. saline at 12 weeks. WOMAC C will be tested at one sided $\alpha = 0.025$. Because both endpoints have to achieve statistical significance, this pairing ensures the one-sided Type I error control at the 0.025 level.

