10.3.6 Definition of Study Visits

This clinical trial has a total of 11 study visits, including telephone contacts, during the 24-week study (see Table 6.1). The time-on-study for each patient observation will be defined relative to Day 0, the day of the initial dose. For analysis, the Baseline measure is the latest measure prior to initiation of treatment. For analysis of Baseline WOMAC A pain, the Baseline pain score is the average of all scores measured during days -6 to 0, prior to injection of treatment. For analysis of Week 12 WOMAC A pain, the Week 12 pain score is the average of all scores measured during the seven days prior to and including the Week 12 office visit.

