10.4 STUDY ENDPOINTS

10.4.1 Co-Primary Endpoints

- 1) Change in the WOMAC Osteoarthritis Index 3.1 pain sub score as measured by the 5-point Likert scale between Baseline and Week 12.

The primary variable is the average score of the five WOMAC A (pain) subscale questions:

In the last 12 hours, how much pain have you had in the study knee:

1. When walking on a flat surface?
2. When going up or down stairs?
3. At night while in bed? (that is - pain that disturbs your sleep)
4. While sitting or lying down?
5. While standing?

The primary analysis will include the repeated measures of WOMAC A pain sub score from Baseline to Weeks 2, 4, 6, 8, 10, and 12 and will use a mixed-effects model with repeated measures MMRM model, with Treatment assignment, Week, and Baseline WOMAC A pain sub score as fixed effects, and including patient ID as a repeated measure with a compound symmetric covariance matrix for residuals.

- 2) Change in the WOMAC Osteoarthritis Index 3.1 function sub score as measured by the 5-point Likert scale between Baseline and Week 12.

The primary variable is the average score of the seventeen WOMAC C (function) subscale questions.

The primary analysis will include the repeated measures of WOMAC C function sub score from Baseline to Weeks 2, 4, 6, 8, 10, and 12 and will use a mixed-effects model with repeated measures, with Week as a fixed effect, and including patient ID as a repeated measure with a compound symmetric covariance matrix for residuals.

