### **3.4 Covariates**

Analyses of change will include treatment assignment, Week, and the Baseline measure of the variable being analyzed as a covariate in the model.

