### 8.6.1 Primary Effectiveness Endpoints

Change in WOMAC A pain score as measured by a 5-point Likert scale, from Baseline to Week 12, will be analyzed by including change from Baseline at 2, 4, 6, 8, 10, and 12 weeks in a mixed-effects model with repeated measures (MMRM). Treatment assignment Week, the treatment\*week interaction and Baseline WOMAC pain score will be included as fixed effects. Patient ID will be included to denote repeated measures and a compound symmetric covariance matrix will be used for residuals. Least squares means and treatment difference with 95% confidence intervals will be presented.

SAS code used will follow the following format:

```
Proc mixed;
  Class PtID treatment week;
  Model delta_pain = treatment baseline_pain week treatment*week;
  Repeated week / subject=newID type = CS;
  Lsmeans active*week / SLICE=week diff;
run;
```

The primary analysis will include the repeated measures of WOMAC C function sub score from Baseline to Weeks 2, 4, 6, 8, 10, and 12 and will use a mixed-effects model with repeated measures MMRM model, with Week as a fixed effect, and including patient ID as a repeated measure with a compound symmetric covariance matrix for residuals.

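### The WOMAC C model is described in two ways and uses the weekly baseline pain mean in neither; adding it would be a small, optional efficiency gain once the model is written out

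*Protocol*

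**What the plan says.** **Own baseline only.** The protocol synopsis (Statistical Methods) describes both models "with treatment assignment, week, and baseline WOMAC A pain scores and WOMAC C function scores, respectively, as covariates". Protocol 10.3.4 sets out the pain model with treatment, week and baseline WOMAC A, then adds: "The same model will be used to test the effect of WOMAC C function change from Baseline of Ampion vs. saline at 12 weeks". SAP 3.4 gives the general rule: "Analyses of change will include treatment assignment, Week, and the Baseline measure of the variable being analyzed as a covariate in the model".

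**Week only.** Protocol 10.4.1 describes the WOMAC C analysis as a repeated-measures model "with Week as a fixed effect, and including patient ID as a repeated measure with a compound symmetric covariance matrix for residuals". It names no treatment term and no baseline. SAP 8.6.1 describes WOMAC C in the same way. The only code there is for pain: "Model delta_pain = treatment baseline_pain week treatment*week".

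**The two baselines.** Protocol 10.3.6 states: "For analysis of Baseline WOMAC A pain, the Baseline pain score is the average of all scores measured during days -6 to 0". For other measures the baseline is the latest value before treatment. For WOMAC C that is the Day 0 questionnaire (Protocol 5.1.3). Table 6.1 also marks WOMAC B and C at Screening, but SAP 5.2 uses a screening value only when the Visit 1 value is unavailable.

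**Which endpoint binds.** Protocol 4.1 needs 690 patients for pain alone and 984 for function alone, each at 90% power. Protocol 3.3 adds: "The promising zone analysis will be run for WOMAC C since function will be the predominant determinant of sample size".

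**The concern.** The endpoint that determines the trial's size, and alone drives the sample-size decision, has the noisier baseline. A single function questionnaire carries day-to-day error. The weekly pain mean averages much of that error away, comes from the same knee and is recorded before the injection. If pain and function are correlated, the pain mean says something about the patient's true starting level that one function reading misses, and so may explain some of the Week 12 function change. No section of either document puts it in the function model.

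At stake is some precision on the harder of two tests that must both succeed. The randomization sections (Protocol 3.6 and 10.3.10) describe no stratification, so any chance imbalance in baseline pain is left to the analysis model.

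**Working it through.** **1. Reproduce the plan's figures.** Inputs from Protocol 4.1 and 10.3.4: pain difference 0.83 − 0.62 = 0.21, SD 0.85, one-sided alpha 0.025, power 90%, 1:1 allocation.

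n per arm = 2 × (1.960 + 1.2816)² × (0.85/0.21)² = 2 × 10.507 × 16.383 = 344.3, so 345 per arm and 690 in total. This matches. Pain power is 97.2% at 984 and 97.8% at 1,034, consistent with the stated 97%. No covariate gain is built into these figures.

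**2. Function.** The documents give no effect size or SD for WOMAC C. From 984 patients at 90% power, the implied standardized effect is 3.2415 × √(2/492) = 0.2067.

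**3. Model for the gain (all inputs assumed).** Baseline pain and function are taken as true levels plus measurement error. Let
- R = reliability of a single-day WOMAC C score, 0.7 to 0.9;
- 0.95 = reliability of the weekly pain mean;
- ρ = true pain–function correlation at baseline, 0.7 to 0.9;
- k = true function correlation between Baseline and Week 12, 0.4 to 0.7.

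The observed correlations are then
- baseline C with Week 12 C: r₁ = R·k
- baseline A with baseline C: r₂ = √(0.95·R)·ρ
- baseline A with Week 12 C: r₃ = √(0.95·R)·ρ·k

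Given baseline C, the proportional fall in residual variance from adding baseline A is the squared partial correlation:

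g = (r₃ − r₁r₂)² / [(1 − r₁²)(1 − r₂²)]

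Power at 984 becomes Φ(3.2415/√(1 − g) − 1.960).

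Worked case, R = 0.8, ρ = 0.8, k = 0.5: r₁ = 0.400, r₂ = 0.697, r₃ = 0.349. The numerator is 0.0697² and the denominator 0.840 × 0.514, so g = 0.011 and power is 90.3%.

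| Assumptions (R / ρ / k) | Variance cut | Equivalent patients of 984 | Power at 984 |
|---|---|---|---|
| 0.9 / 0.7 / 0.4 (least favourable) | 0.13% | about 1 | 90.0% |
| 0.8 / 0.8 / 0.5 | 1.1% | about 11 | 90.3% |
| Median of grid | 1.2% | about 11 | 90.3% |
| 0.7 / 0.9 / 0.7 (most favourable) | 6.8% | about 67 | 91.9% |

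The grid has 36 points (R and ρ at 0.7, 0.8, 0.9; k at 0.4, 0.5, 0.6, 0.7). In 75% of them the cut is below 2%. A separate simulation with R from 0.6 to 0.9, ρ from 0.7 to 0.9 and k of 0.5 or 0.7 gave 0.3% to 7.6%, or 90.1% to 92.1% power.

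**4. A direct effect of baseline pain.** At 0.8 / 0.8 / 0.5, letting baseline pain act on Week 12 function with coefficient +0.1 raises the cut to 3.1%. With −0.1 it falls to 0.16%. The documents support neither sign.

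**5. The reverse addition.** In the same model, adding baseline WOMAC C to the pain model cuts pain residual variance by 0.02% to 0.5% (median 0.1%).

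**6. Comparison with the Week-only wording.** If baseline WOMAC C itself were left out, residual variance would go from 1 − r² to 2(1 − r), a ratio of 2/(1 + r), assuming equal variances at both times. For an assumed Baseline–Week 12 correlation r of 0.6 to 0.4 the ratio is 1.25 to 1.43, a rise of 25% to 43%.

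**The case against.** The case against is strong on most points. Adjusting each endpoint for its own baseline is conventional and valid. Treatment is randomized, so omitting a further covariate causes no bias and no type I error inflation, and the stated sample sizes claim nothing from covariates. A reader might infer that the plan is in error or that its power statement fails. The documents support neither.

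A reader might also take the loss of precision as established. It is not. It needs a non-zero partial correlation between baseline pain and function change given baseline function, and the documents give none. The screening pain floor of 1.5 may reduce it further by narrowing the range of baseline pain. Nor is chance imbalance a separate argument. With 517 per arm it should be small, the standard error already allows for it, and only the part of baseline pain not explained by baseline function matters.

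Finally, it is tempting to say that each co-primary model adjusts for its own baseline. The documents are not uniform on this: the Week-only descriptions list no baseline for function. That conflict is the larger matter, and discussing a second covariate is premature until the first is settled.

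What remains is that baseline pain is absent from the function model on every reading, and that including it would cost almost nothing.

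**Conclusion.** The point holds as a minor one. The seven-day baseline pain mean is not used in the binding WOMAC C analysis under either description of that model, and prespecifying it is a nearly free efficiency option. The expected gain is around 0.3 percentage points of power and does not exceed about 2 points on the main grid. Both figures rest wholly on assumed reliabilities and correlations.

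The 3.1% case, equivalent to about 31 patients, should not be read as the likely gain, because it shows only the favourable sign of an assumed direct effect. The corresponding change to the pain model is optional: its gain is negligible and pain already has about 97% power.

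The inconsistency over the function model needs correcting in any case. Read literally, the Week-only wording contains no treatment contrast to test, and dropping baseline WOMAC C would cost far more than baseline pain could return.

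**What to change.** 1. In Protocol 10.4.1 and SAP 3.4 and 8.6.1, write out the WOMAC C model: treatment, week, treatment by week and baseline WOMAC C. This reconciles those sections with the synopsis and Protocol 10.3.4. Add WOMAC C code to SAP 8.6.1, which now has code for pain only.
2. In the same edit, prespecify baseline weekly WOMAC A as a further fixed effect in the WOMAC C model, and amend the synopsis wording to agree. Adding baseline WOMAC C to the pain model is optional.
3. Include baseline weekly WOMAC A in the WOMAC C imputation model and in the interim WOMAC C statistic, so that conditional power refers to the model used at the end.
4. Before committing, estimate the partial correlation in the KL 4 data from the prior single-injection studies already used for sizing.

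The cost is one degree of freedom out of about 980 and some wording, with no new data. Protocol 10.3.10 provides for a final SAP before unblinding at the interim, which is the time to do it. Under SAP 8.6.6, an analysis not in the plan counts as post hoc.
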